6.3.2. MR Scanning Procedures

Monitoring Subjects during MR Scanning

During MRI scanning, subjects will be monitored in real-time using a properly functioning Expression MRI Patient Monitor (Invivo, Corp; Orlando, FL, USA). The subject will be observed all times during the MR scan by a qualified medical professional (nurse, neonatologist, and/or other medical doctor qualified for neonatal/infant care) on the study staff who shall remain in the magnet room with the subject during scanning. The observing staff should remain in a position where they can readily observe the subject and monitor and, if necessary, contact the scan operator during the scanning session.

A conservative threshold for body temperature alarm is selected, as such that body temperature change is sufficient to trigger an alarm (0.5°C above the pre-scanning baseline temperature) is not in itself considered a clinically significant risk to patients; these patients will be evaluated by a medically qualified member of the study staff for any other possible signs or symptoms and they will determine whether an AE has occurred as per the standard procedures described in Section 11 – Complaint Handling and Adverse Event Reporting.

If a body temperature alarm on the monitor is triggered at any time during scanning, the study staff should stop the scan series. Then, the following elements will be documented as part of study data for each such alarm occurrence:

- the time of alarm
- *Alarm Temperature* the body temperature at time of alarm, based on body temperature measurement made with the Expression Monitor (Invivo), as follows:
 - temperature measurement value
 - anatomical area of measure (specific area of skin surface).
- the time it takes to return to pre-scanning baseline temperature (minutes/seconds)

Note: In the event that the baby's body temperature does not return to a level at or below the pre-scanning baseline temperature within the study scanning period (not to exceed 60 minutes from first localizer to end of scanning) patient scanning will be discontinued (if collected, the patient's data collected up until this time may still be used for study purposes, and pre-scanning information may still be recorded about the patient)

- any conditions observed that possibly contributed to temperature rise, such as swaddling, environmental conditions, distress, or scanning conditions? (Y/N, if yes explain)
- decision to continue the scan session (do not continue after first alarm)? (Y/N)
- *Continuing Temperature* the body temperature at the time of scanning was continued using an Expression Monitor (Invivo) as follows:
 - temperature measurement value
 - anatomical area of measure (specific area of skin surface).

A medically qualified investigator should evaluate each patient to determine if it is safe to continue scanning once the patient's body temperature returns to pre-scanning baseline temperature or lower in the event of an alarm. If an alarm is triggered more than once during a single scan session, scanning will be discontinued. If collected, the patient's data collected up until this time may still be used for study purposes, and post-scanning information may still be recorded about the patient.

Subject MR Scanning Procedures

The total time starting from the start of the first localizer to the time at the end of the last scan will not exceed sixty (60) minutes. Additional time may be required for setup and removal of the patient.

The scan operator will:

- a. enter the subject's anonymized ID number in the "Subject Name" and "Subject ID" field in the MR scanner's user interface.
- b. enter the subject's weight in the MR scanner's user interface.

In addition to the scan operator, a member of the study staff cleared to enter the MR magnet room will remain in the MR suite at all times when a subject is present in order to assist the scan operator should an emergency situation arise

MR Scanning Information

For each scanning session, the following scanning information shall be recorded by the scan operator, including the following:

- *MR Procedure Documentation* Version Number
- Phase of Scanning (Phase 1 or Phase 2)
- Subject number
- Date of scanning
- Was the subject sedated for standard of care reasons prior to scanning (Y/N)
- Time and type of clinically indicated sedative administration

Note: No sedatives will be administered for the purpose of this study. Check yes only if the subject was previously administered clinically indicated sedative(s) within the last 24 hours prior to scanning.

- Start and End time of scanning determined by time just prior to first localize and time at end of last scan (on 24 hour clock)

- Scan operator name and signature
- Anatomy scanned (i.e. neurological (head/neck/spine) Was subject fed before (<1 hour) prior to scanning? (Y/N)
- Did subject require pacifying during scan? (Y/N) Were there any repeat scans done due to motion artefacts caused by subject voluntary motion? (Y/N)
- Were there any recoverable system errors or failures during the scanning session? (Y/N) If Yes, please describe.
- Comment: Describe any image features which may have negatively affected the image quality including items such as, but not limited to, artefacts, tissue contrast, noise etc.
- Additional Sponsor-Requested Assessments
 - Modifiable CRF fields (10 blank “Assessment Title” lines with associated 1-5 Likert scales) will be provided on the CRF to accommodate Sponsor-requested elements that may be specified for each *MR Procedure Document*
 - The investigator is responsible for being aware of any additional elements required by each *MR Procedure Document* version number.
 - The investigational site(s) will be notified of any additional instructions for completing comments, and will be responsible for completing the comments field as instructed after appropriate training and instruction has been provided by the Sponsor.
- Investigator Comments
 - The investigator is encouraged to make additional comments on any atypical or exceptional events that occur during subject scanning.
 - During the study, the Sponsor may provide additional instructions for recording specific types of conditions or information in the comments field at its discretion as part of an *MR Procedure Document*
 - The study staff will be responsible for completing the comments field as instructed in the applicable *MR Procedure Document* (as indicated by version number) after appropriate training and instruction has been provided by the Sponsor.

In Phase 1, the Sponsor’s engineering representative, if present, may optionally record any applicable comments on a dedicated CRF page.

MR Scanner Issues

Issues that occur during the scanning session: In the event of recoverable issues during the scan session:

- a. the scan operator will generate an issue report according to the instructions provided by the Sponsor,
- b. Data may be collected from the MR scanner by the Sponsor’s authorized engineering representative.

Note: Any Sponsor engineer involved at the site will be trained on the clinical protocol. These Sponsor engineers are qualified to answer technical questions about the device, but will not be authorized to provide training, retraining, or answer study conduct questions raised by

study staff, such as issues with informed consent or other protocol issues/questions. Study conduct questions that are non-technical in nature should be referred to the Clinical Affairs Project Manager. Device use, installation, operation, maintenance, and other technical questions may be addressed with on-site engineers.

Non-recoverable malfunctions: Non-recoverable malfunctions will be considered those that are not resolved by the scan operator rebooting/resetting the system. In the event of a non-recoverable MR system malfunction:

- a. the scan session will be stopped,
- b. the subject will be removed from the MR environment and returned to their standard of care environment,
- c. the equipment will be assessed by the Sponsor, and
- d. The Sponsor must authorize that the device may be used prior to scanning additional clinical subjects.

6.3.3. Post-scanning MR Procedures

Post-scanning Subject Information

Post-scanning information will be recorded for all subjects:

- ~~Postscanning temperature~~ Body temperature, immediately before removal from the MR scanner (postscan body temperature), body temperature measurement made with an Expression Monitor (Invivo) and anatomical area of measure (specific area of skin surface).
 - ~~Final temperature~~ Body temperature measured after transport and just before the subject is placed into the routine care environment, as follows:
 - temperature measurement value
 - device type (record standard of care device), and
 - anatomical area of measure (specific area of skin surface)
- Note:** It is preferred that the same method as used for the ~~pre-transport Temperature~~
- End of Enrollment Time: Time when the patient is returned to the clinical care area and all Sponsor provided device components (i.e., Swaddle, Invivo monitor, pads, etc.) have been removed from the subject.
 - Additional Sponsor Requested Assessments
 - CRF fields (10 blank "Assessment Title" lines with associated Likert scales) will be provided on the CRF to accommodate Sponsor requested elements that may be specified for each *MR Procedure Document*
 - The investigator is responsible for being aware of any additional elements required by each *MR Procedure Document* version number.
 - The investigational site(s) will be notified of any additional instructions for completing comments, and will be responsible for completing the comments field as instructed after appropriate training and instruction has been provided by the Sponsor.
 - Comments
 - The investigator is encouraged to make additional comments on any atypical or exceptional events that occur during subject scanning. During the study, the Sponsor may provide additional instructions for recording specific types of conditions or information in the comments field at its discretion as part of

The study staff will be responsible for completing the comments field as instructed in the applicable *MR Procedure Document* (indicated by version number) after appropriate training and instruction has been provided by the Sponsor

Post Scan Environmental Conditions

At the end of the last scan series when the scan operator enters the scan room to remove the subject from the MR device, the scan operator will record

- Scan room temperature
- Number of personnel required to remove subject from the scanner and undock the cart/table from the MR scanner and transport the MR table out of the scan room and into the MRI preparation room.

Post Scan Operator Assessments

For each subject, a designated study staff member present during the MR scan session will complete the usability survey for all applicable device components ([Appendix F – Example of 3.0T Neonatal MRI Investigational Device User Experience Questionnaire](#); [Appendix G – Example of Single-Use Disposable Swaddle User Experience Questionnaire](#)). More than one study staff may collaborate to complete these surveys, but only one survey form should be completed based on the consensus between all participating study staff. The Sponsor's representative may also collect observational comments during human scanning.

6.3.4. Evaluations

Performance Evaluation

Image sets will be labelled according to subject identification number. Images will be evaluated as evaluable (diagnostic) or non-evaluable (non-diagnostic) by two evaluators, and then evaluable images will be read for image quality by a separate reader, as shown in [Figure 2](#).

[figure not shown]

Figure 2– Flowchart of performance evaluation. Determination of evaluable/non-evaluable for diagnostic purposes will be used as the primary performance measure. All secondary Image Quality Assessments will be descriptively summarized.

MR image datasets for each subject will be evaluated twice by two delegated radiologists serving as image evaluators (Evaluator 1 and Evaluator 2) as:

- Evaluable (Diagnostic Quality)⁶, or
- Non-evaluable (Non-Diagnostic quality)

The evaluations and printed name and signature of the image evaluator(s) will be recorded to an Evaluator CRF. In the event that the two evaluators (Evaluator 1 and Evaluator 2) disagree on whether an image is evaluable or non-evaluable, a third medically qualified reader (Reader 1) will arbitrate to provide an evaluable/non-evaluable decision, which will be recorded to the Reader CRF and treated as the final decision for the image set.

Image Quality Assessments

All evaluable images will be further examined by a single reader (Reader 1) that may be the PI or a qualified delegated radiologist for image quality on a 1-5 Likert Scale,⁷ as follows:

- Overall image quality

⁶ An image set may be considered of diagnostic quality if it contains images suitable for diagnosis (not all images views are typically required to be diagnostic based on specific scanning circumstances, so long as applicable views necessary for diagnosis are present)

⁷ Likert Scale of 1-5, where:

- 1 = Very Poor
- 2 = Poor
- 3 = Neutral
- 4 = Good
- 5 = Excellent

Note For image quality assessment, scores of 3, 4, or 5 will be considered diagnostic quality, and scores of 1 and 2 will be considered nondiagnostic quality.

- Image contrast
- Presence of artefacts
- Signal to noise ratio (SNR)
- Tissue contrast
- Fat/water homogeneity
- Additional Sponsor-Requested Assessments
 - CRF fields (10 blank “Assessment Title” lines with associated 1-5 Likert scales) will be provided on the CRF to accommodate Sponsor-requested elements that may be specified for each *MR Procedure Document*
 - The investigator is responsible for being aware of any additional elements required by each *MR Procedure Document* version number.
 - The investigational site(s) will be notified of any additional instructions for completing comments, and will be responsible for completing the comments field as instructed after appropriate training and instruction has been provided by the Sponsor.

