4.2. Controls and Minimization of Bias

The following bias control methods are being employed in this study:

- a. Selection bias will be limited by consecutively enrolling subjects meeting the inclusion/exclusion criteria

- b. Spectrum bias will be limited by using a population expected to be representative of the general population at the investigational site, without regard for gender, race, or ethnicity.
- c. Reader bias will be limited by ensuring that evaluators and readers making performance assessments are separate radiologists (not the PI or neonatologist).

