5.1.2. Special Considerations for Enrolment

The following special considerations apply to subject enrolment in both Phase 1 and Phase 2.

1. **Incomplete Datasets:** Datasets may be incomplete due to factors such as noise, sequence failure, or patient movement. Datasets determined to be incomplete or non-evaluable by the investigator will not be counted towards the total required datasets for the purposes of determining quota fulfilment (per protocol population) but these will be reported in the total patient enrolment in the study final report.

(intent-to-treat population). Both complete and incomplete images and data will be stored and provided to the Sponsor for engineering purposes.

2. **Changes to Quota Requirements during the Study:** The Sponsor reserves the right to change quota or Phase dataset number requirements at its discretion and for any reason within the set patient enrolment maximum. The Sponsor will notify the investigational site in writing of any changes in enrolment quotas.

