6.6. Study Flowchart

Table 3– Flowchart detailing the data elements to be collected during each part of the study

Procedure/ Data Element	General Procedures (time interval)	Recruitment / Screening	Pre-Scan	MR Scanning	Post-Scan	Reader/ Evaluator Assessments
Quality Control Scan	Sponsor-set interval(s) ¹					
Specific Absorption Rate (SAR) Scans				X		
Running MR Scan Session Log	Daily verification			X		
MR Procedure Documents (Prepared by Sponsor)	Prior to enrolling first subject, thereafter at Sponsor-set regular interval ¹					
Qualitative Investigator Summary (Prepared by PI)	Within ~3 business days of completing MR Procedure document activities				X	
Inclusion/Exclusion		X				
Collect subject Information			X	X	X	
MR Safety (subject and any persons accompanying him or her into scan room)		X	X	X	X	
Application/Removal of Swaddling (if used)/Padding			X		X	
Transport			X		X	
Environmental conditions			X		X	
MR Procedure Document Identification (Version number)				X		
MR Scanning Information				X		
Software/Hardware components used				X (Phase 1 only) ²		
MR Scanner Technical Issues/Malfunctions				X		
Additional Sponsor-Requested Assessments			X	X	X	X(reader only)

Procedure/ Data Element	General Procedures (time interval)	Recruitment / Screening	Pre-Scan	MR Scanning	Post-Scan	Reader/ Evaluator Assessments
			(defined in MR Procedure Doc)	(defined in MR Procedure Doc)	(defined in MR Procedure Doc)	(defined in MR Procedure Doc)
MR Images and Data				X	X	X (access to)
Evaluable (Diagnostic)/Non-evaluable (Non-diagnostic) Assessment						X (reader and evaluators)
Image Quality Assessments						X (reader only)
Overall image quality (based on investigator's experience)						X (reader only)
Image contrast						X (reader only)
Presence of artefacts						X (reader only)
Signal to noise ratio (SNR)						X (reader only)
Tissue contrast						X (reader only)
Fat/water separation						X (reader only)
AEs/SAEs			X (From placement on swaddle, if used, or if not used from removal from clinical care environment to MR)	X	X (to removal from swaddle/padding and return to clinical care environment)	
MR System Errors/Issues				X		
MR Component/Accessories Errors/Issues			X	X	X	
Usability Assessments						
System Usability Scale (SUS)	Operator completes at end-of-scanning for					

Procedure/ Data Element	General Procedures (time interval)	Recruitment / Screening	Pre-Scan	MR Scanning	Post-Scan	Reader/ Evaluator Assessments

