APPENDIX M: AMENDMENT TO PROTOCOL VERSION 6.0

Purpose: This amendment document describes the changes from protocol version 6.0 to 7.0, as follows:

1. To clarify that the two (2) radiologists will act as image evaluators (rather than the PI and a neonatologist). This is done to minimize bias, as the PI and neonatologist may be directly involved in study acquisitions based on specific site practices.
2. Clarifies the responsibilities of evaluators and readers in this study in figures and flowcharts, for clarity only (this does not change the original intent or design of the study, other than as described in #1 above).
3. To clarify the roles of participating physicians and neonatologists in the study procedure and assessments.
4. To clarify the procedures for screenings subjects for enrolment and verify MR safety prior to study procedures.

The following amendments were made to version 6.0 to produce version 7.0. Point-by

-point revisions are shown as additions in double-underline (double-underline) and deletions in strikethrough (~~strikethrough~~) for each change made in this amendment for the previous version.

Item	Section	Revision or Clarification	Justification
57	Study Synopsis	Duration: The study plans to actively enrol patients for approximately 24 months.	Removed the descriptor "active" describing the EC/IRB approved protocol as this is not meant to correspond with the "active" enrolment period for AE reporting purposes. This term is removed to clarify this intent.
58	Section 2.6. Disposition of the Device/Product	When scanning under all active EC/IRB approved study protocols is completed, the following actions will be conducted:	Removed the descriptor "active" describing the EC/IRB approved protocol as this is not meant to correspond with the "active" enrolment period for AE reporting purposes. This term is removed to clarify this intent.

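### Section 6.3.4 allows the PI to be Reader 1, who arbitrates the primary performance measure and alone scores image quality, although Section 4.2(c) excludes the PI from that role

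*Combined protocol and SAP*

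**What the plan says.** Section 4.2(c) lists a bias control: "Reader bias will be limited by ensuring that evaluators and readers making performance assessments are separate radiologists (not the PI or neonatologist". It names readers as well as evaluators.

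Section 6.3.4 sets out the procedure. Two delegated radiologists, Evaluator 1 and Evaluator 2, each call an image set evaluable or non-evaluable. On the status of that call: "Determination of evaluable/non-evaluable for diagnostic purposes will be used as the primary performance measure". If the two disagree, "a third medically qualified reader (Reader 1) will arbitrate to provide an evaluable/non-evaluable decision", and the result is "treated as the final decision for the image set". On image quality, the same section says: "All evaluable images will be further examined by a single reader (Reader 1) that may be the PI or a qualified delegated radiologist".

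The row for the evaluable/non-evaluable assessment in Table 3 (Section 6.6) reads "X (reader and evaluators"; the image-quality rows are for the reader alone.

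Section 5.1.2 has related wording on the quota and the per-protocol population: "Datasets determined to be incomplete or non-evaluable by the investigator will not be counted towards the total required datasets".

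**The concern.** Both statements about the PI are in the current version 7.0 text, and they cannot both be followed if the PI serves as Reader 1. Appendix M gives the reason for taking the evaluator role away from the PI and the neonatologist: "This is done to minimize bias, as the PI and neonatologist may be directly involved in study acquisitions based on specific site practices". The same reason applies to whoever settles a disagreement, and the sets on which two radiologists split are the ones where an independent third opinion matters most. The study is open-label and at one site, and the call is a subjective yes/no judgement.

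At stake is the credibility of the descriptive proportion that serves as the primary performance evidence, and of the secondary image-quality scores. Section 3.2 allows summaries from both phases to go to regulators.

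**Working it through.** **Comparing the passages**

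| Question | Section 4.2(c) | Section 6.3.4 |
|---|---|---|
| May the PI be a reader? | No, for performance assessments | Yes, as Reader 1 |
| Must the arbiter be a radiologist? | Yes | Only medically qualified |
| Who decides discordant sets? | Someone other than the PI | Reader 1, with final effect |
| Who scores image quality? | Not the PI, if this counts as a performance assessment | Reader 1 alone, possibly the PI |

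The link between the PI option and the primary measure is the label Reader 1. Section 6.3.4 uses it for both the arbiter and the image-quality reader, and the plan names no other reader. Table 3 agrees, since it gives the reader a part in the evaluable/non-evaluable assessment. Nothing in the text has a PI acting as Reader 1 hand arbitration to someone else. Figure 2, the flowchart of this process, was not available in the text reviewed.

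**The plan's own figure**

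Section 8.1.1 uses 82% evaluable, 20% dropout and a target of 30 + 5 = 35 evaluable sets.

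N = 35 / (0.82 × 0.80) = 35 / 0.656 = 53.35.

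The plan states a minimum of 53 and rounds it up to 60. The figure reproduces, and the point made here does not depend on it.

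**How many primary calls could reach Reader 1**

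The documents give no evaluator agreement rate, so the following is illustrative. Assumptions: one set per subject; all dropout occurs before scanning; each evaluator rates 82% of sets evaluable; kappa is 0.8, 0.6 or 0.4.

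- Scanned sets: 53 × 0.80 = 42.4; at the maximum enrolment, 60 × 0.80 = 48.
- Disagreement expected by chance: 2 × 0.82 × 0.18 = 0.2952.
- Disagreement at a given kappa: d = (1 − kappa) × 0.2952.
- If every arbitration went the same way, the primary proportion would lie at 0.82 ± d/2.

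| Kappa (assumed) | Disagreement d | Arbitrated of 42.4 | Arbitrated of 48 | Settled without Reader 1 | Extreme range of the proportion |
|---|---|---|---|---|---|
| 0.8 | 5.9% | 2.5 | 2.8 | 94.1% | 79.0% to 85.0% |
| 0.6 | 11.8% | 5.0 | 5.7 | 88.2% | 76.1% to 87.9% |
| 0.4 | 17.7% | 7.5 | 8.5 | 82.3% | 73.1% to 90.9% |

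The counts and ranges are the same for any arbiter. They show where the control is not guaranteed and do not estimate bias from the PI.

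**Image-quality scores**

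Reader 1 scores every evaluable set, so the possible reach is 35 of 35 at target.

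**Quota wording**

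Section 5.1.2 lets the investigator determine which sets are non-evaluable for the quota and the per-protocol population. Section 6.3.4 gives the final determination to the evaluators and Reader 1. The plan does not say which governs the quota count.

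**The case against.** The best counter-argument is that the two sections can be read together. The PI option appears only in the sentence on image quality, which Section 6.3.4 treats as secondary, and Section 3.4.1 defines performance through the evaluable/non-evaluable proportion. On that reading, Section 4.2(c) bars the PI from the primary call and leaves the PI free to score image quality.

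This does not remove the conflict. It would need two different people behind the single label Reader 1, or a hand-over rule that the plan lacks. The argument has more force for the image-quality scores taken alone. Even there, Section 6.2.1 and the sample form in Appendix B list overall image quality among the Likert assessments of performance, and the footnote in Section 6.3.4 ties those scores to diagnostic quality.

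Other points stand:

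- The PI role is permitted, not required, and touches the primary measure only after two non-PI radiologists have disagreed.
- The kappa values and the timing of dropout are assumptions, and 53 is the calculated minimum, not the enrolment maximum.
- The investigator in Section 5.1.2 is not said to be the PI. That wording is a related gap and does not itself show that the PI arbitrates.
- Deleting the PI option also withdraws a permission for secondary scoring that the sponsor may have intended, so a narrower remedy should be offered.

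**Conclusion.** The concern holds and should be fixed. The plan states that readers assessing performance are not the PI, yet its procedure lets the PI make the final decision on discordant sets for the primary measure and be the sole scorer of image quality. The contradiction is established from the text alone.

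Its size depends on the assumptions above: roughly 6% to 18% of primary calls could go to Reader 1, and 82% to 94% keep the control in full. The consequence is limited to the credibility of a descriptive proportion and of the secondary scores. Section 3.1 states that no hypothesis is tested, Section 8.4 sets no numeric success threshold, and the sample size is unchanged.

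**What to change.** 1. In Section 6.3.4, remove the PI as a permitted Reader 1, so that Reader 1 is a qualified delegated radiologist as Section 4.2(c) requires. At minimum, state that the PI may not arbitrate the evaluable/non-evaluable decision, and reword Section 4.2(c) so that it claims no more than the procedure delivers.
2. In Section 5.1.2, state that evaluable status for the quota and the per-protocol population is the final decision under Section 6.3.4, while the investigator continues to identify incomplete datasets.
3. Optionally, report how many sets were arbitrated. The Evaluator and Reader CRFs already hold this, so no new data are needed.

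The cost is protocol wording, plus a radiologist other than the PI and the two evaluators who is available to arbitrate. Section 4.2(c) already commits to that person; what is lost is the option of using the PI as a substitute.
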